### 5.1.3 Exploratory Objectives

To explore the relationships among participant characteristics, study medication, and clinical outcomes, we define the following pre-specified exploratory objectives:

1. To identify baseline features that predict treatment responsiveness, disease progression and the course of lung and skin disease over time.
2. To identify biomarkers that predict disease features, treatment responsiveness, disease progression and the course of lung and skin disease over time.

## 5.2 Endpoints

### 5.2.1 Primary Endpoint

The primary endpoint is the change from baseline, measured at 3-month intervals, in the mean forced vital capacity (represented as the percentage of the age-, height-, gender- and race-adjusted predicted value, i.e. FVC-%) over the course of the 18-month double-blind treatment period.

### 5.2.2 Secondary Endpoints

1. The change from baseline to 18 months, measured at 3-month intervals, over the course of the 18-month treatment period in:
  - a. Single-breath diffusing capacity for carbon monoxide (DLCO), calculated as a percent of the age-, height-, gender-, race- and hemoglobin-adjusted predicted value (DLCOHb-%).
  - b. Modified Rodnan Skin Score (mRSS).
  - c. Forced vital capacity volume (FVC, in ml)
  - d. St. George Respiratory Questionnaire (SGRQ)
2. Transition Dyspnea Index at 18 months, measured at 3-month intervals, over the course of the 18-month treatment period.
3. The change from baseline to 18 months, measured at 6-month intervals, over the course of the 18-month treatment period in Health assessment questionnaire modified for scleroderma (SHAQ) includes:
  - a. HAQ-DI calculated without aids/devices
  - b. Scleroderma-HAQ-DI visual analogue scales (VAS) assessing burden of pain, burden of digital ulcers, Raynaud's, GI involvement, breathing, and overall disease
4. The change from screening to month 18 in quantitative HRCT measures of SSc-ILD which specifically include:
  - a. Quantitative lung fibrosis score in the whole lung (QLF-WL).
  - b. Quantitative lung fibrosis score in the lobe of maximal involvement (QLF-LM).
  - c. Quantitative interstitial lung disease score in the whole lung (QILD-WL).
  - d. Quantitative interstitial lung disease score in the lobe of maximal involvement (QILD-LM).
  - e. Total lung capacity at maximum inspiration (HRCT-TLC)
5. The time (in months) required for each treatment arm to achieve a 3.0% (absolute) or greater improvement from baseline in the FVC-% over the 18-month treatment period.

6. The proportion of participants in each treatment arm achieving greater than a 5% (absolute) improvement from baseline in FVC-% over the 18-month treatment period.
7. The proportion of participants in each treatment arm achieving absolute change of FVC-% from baseline to month 18 as:
  - a. Improvements by up to 5%, from 5% to <10% and from 10% to <15% or worsening by up to 5%, from 5% to <10% and from 10% to <15%.
  - b. Positive responders (improved at least 3% or more), negative responders (worsened at least 3% or more), and stable (> -3% to < 3%)
  - c. Responder (> 0) and non-responders ( $\leq 0$ ).
8. The proportion of participants in each treatment arm achieving absolute change of mRSS from baseline to month 18 as:
  - a. Using 4 points increments: worsen (1 to 4,  $\geq 5$ ), no change (=0), improved ( $\leq -13, -12$  to -9, -8 to -5, -4 to -1).
  - b. Improved (< -5), no change (-5 to 5), and decreased (> 5).
9. The proportion of participants in each treatment arm achieving the TDI focal score at month 18 as :
  - a. Improved by 1-3, 4-6 and 7-9 points, no change (0) and worsened by 1-3, 4-6 and 7-9 points.
  - b. Improved (>0), no change, deterioration (<0).
10. Tolerability and toxicity of combined MMF and Plac vs MMF and PFD over the course of the 18-month treatment period.
  - a. The time from start of treatment to withdrawal or removal from active drug therapy for any reason.
  - b. Number of participants with treatment-emergent adverse events related to study medication as assessed by system organ classification using preferred Medical Dictionary for Regulatory Activities (MedDRA) terms.

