In order to better understand the modeled outcomes, frequency distribution histograms were prepared from the un-modeled outcome data in which the subject-by-subject change in FVC-% from baseline to 24 months were plotted for the two treatment arms in increments of a 5% improvement or worsening from baseline (**Figure 2.1.2f**). Very similar to outcomes portrayed by the joint model, the overall change ($\pm SE$) in FVC-% averaged 3.0 ± 1.2 for the CYC arm and 3.3 ± 1.1 for the MMF arm. The majority of subjects in both arms had improving FVC-% values over time (64.7% for CYC, 71.7% for MMF) and no significant difference was identified between treatments ($p=0.55$; Fisher's exact test). Of the 34 patients in the CYC arm and the 38 patients in the MMF arm with a positive change over time, the average ($\pm SE$) improvement was 7.1 ± 0.7 and 7.5 ± 0.9 change in FVC-%, respectively. Of the 17 patients in the CYC arm and the 15 patients in the MMF arm whose FVC-% declined over 24 months, the average ($\pm SE$) decrement was 6.0 ± 1.6 and 6.4 ± 1.6 change in FVC-%, respectively. We noted that the majority of subjects who experienced decrements in lung function belonged to the subset in either arm that had stopped drug treatment prematurely. Similar to the observations from the SLS I study, values for the mRSS decreased (i.e. improved) in 73.6 % of subjects on CYC and 71.7 % of subjects on MMF, with most of these improvements being by ≥ 5 units. Mahler's Transitional Dyspnea Index (TDI) values increased (i.e. improved) by at least 1 unit in 59 % of subjects on CYC and 47.5 % of subjects on MMF, with most of these improvements being by ≥ 3 units in both arms. In most cases these individual improvements exceeded the minimal clinically important changes that have been described for both of these endpoints (22,25,52).

Figure 2.1.2f. Raw unmodeled data from all subjects completing the 24 month evaluation, regardless of whether they stayed on drug therapy or withdrew prematurely from the treatment phase of the protocol, was used to construct a frequency distribution of changes from baseline in FVC-% at 24 months, by treatment arm.

The relatively equivalent efficacy and improved tolerability of MMF, as compared to CYC, make a strong clinical argument for its use as the preferred immunosuppressive medication for SSc-ILD (10,52).

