#### 6.4.2.3 Modified Rodnan Skin Score (mRSS)

The modified Rodnan skin score (mRSS) calculated by summation of skin thickness in 17 different body sites using a 0–3 scale, where 0 = normal, 1 = mild thickness, 2 = moderate thickness and 3 = severe thickness. Total skin score can range from 0 (no thickening) to 51 (severe thickening in all 17 areas). Each body site needs to be scored otherwise total score should not be calculated.

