11. A frequency table and bar chart are used to show the frequency distribution of the change of mRSS from baseline to month 18 categorized in 4 points increments: worsen (1 to 4,  $\geq 5$ ), no change ( $=0$ ), and improved ( $\leq -13$ ,  $-12$  to  $-9$ ,  $-8$  to  $-5$ ,  $-4$  to  $-1$ ) overall and in each treatment group in the completers population, and separately for those who completed the treatment period and those who prematurely discontinued treatment but returned for the 18-month mRSS. A frequency distribution of the change of mRSS is also shown in patients with dcSSc in the completers population. The proportions of participants with improved ( $< -5$ ), no change ( $-5$  to  $5$ ), and decreased ( $> 5$ ) in the change from baseline in mRSS, overall and in each treatment group, are also presented.

12. A frequency table and bar chart are used to show the frequency distribution of the TDI at month 18 categorized as improved by 1-3, 4-6 and 7-9 points, no change (0), and worsened by 1-3, 4-6 and 7-9 points, overall and in each treatment group in the completers population, and separately for those who completed the entire treatment period and those who prematurely discontinued treatment but returned for the 18-month TDI. The proportions of participants with improved ( $>0$ ), no change, and deterioration ( $<0$ ), overall and in each treatment group, are also presented.

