##### f. Change Analyses of Secondary Endpoints

Due to small sample size, instead of considering binary secondary endpoints and using logistic regression, we consider clinically meaningful cutpoints and using the frequency table and bar chart to demonstrate the frequency distribution of the secondary endpoints.

PROTOCOL:

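### The three-class mRSS summary labels skin worsening as 'decreased', and its ±5 edges do not nest with the 4-point classes shown beside it

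*SAP*

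**What the plan says.** SAP 5.2.2 item 8 defines a secondary endpoint from the change in mRSS between baseline and month 18, grouped in two ways.

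- **Item 8a** begins "Using 4 points increments: worsen (1 to 4" and continues with a second worsening class of 5 or more, a no-change class of exactly 0, and four improvement classes: −4 to −1, −8 to −5, −12 to −9, and −13 or lower.
- **Item 8b** uses three classes: "Improved (< -5), no change (-5 to 5), and decreased (> 5").

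SAP 10.2.2 item 11 plans both displays together. The three-class proportions "in the change from baseline in mRSS, overall and in each treatment group, are also presented". Section 14, change f, repeats the same text.

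The direction of the score is not in doubt. SAP 6.4.2.3 sums 17 sites scored 0 to 3 and says "Total skin score can range from 0 (no thickening) to 51 (severe thickening in all 17 areas"). Protocol 2.1.2, describing SLS II, reports that "values for the mRSS decreased (i.e. improved) in 73.6 % of subjects on CYC", and adds "with most of these improvements being by ≥ 5 units".

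**The concern.** There are two faults.

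**The label.** In 8b the class above +5 is a rise in a score where higher is worse. Calling it *decreased* gives it the word that the protocol equates with improvement. A table row with that heading counts participants whose skin got worse, but could be read as counting those whose score fell.

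**The edges.** The two groupings of one variable are to be shown side by side, but they treat a change of exactly 5 points differently. A reader who adds the 8a classes beyond 5 points will not recover the 8b proportions and cannot tell from the table why. On a continuous measure a tie at the edge would hardly matter. On a whole-number score in a small trial, a few people can sit exactly there, and the reported proportions improved and worsened depend on which edge is used.

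**Working it through.** **Step 1. Direction of the label.** SAP 6.4.2.3: 0 is no thickening and 51 is severe thickening. A change above +5 is therefore worsening. Comparable SAP labels agree with that reading: 8a says *worsen*, the TDI grouping in item 9b says *deterioration* for values below 0, and the QILD-WL grouping in 5.2.3 says *worsen* for values above 2%. Only 8b uses *decreased* for the bad direction.

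**Step 2. Do the classes nest?** The score is a sum of integers and is not calculated if any site is missing, so every change is a whole number. Assigning each integer from −51 to +51 to both groupings gives:

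| 8a class | 8a label | 8b class of its members |
|---|---|---|
| ≤ −13 | improved | improved |
| −12 to −9 | improved | improved |
| −8 to −5 | improved | −8 to −6 improved; **−5 no change** |
| −4 to −1 | improved | no change |
| 0 | no change | no change |
| 1 to 4 | worsen | no change |
| ≥ 5 | worsen | **5 no change**; ≥ 6 *decreased* |

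Exactly two 8a classes are split, each by one value. The other five fall wholly within one 8b class. The labels also differ at ±1 to ±4, but there whole 8a classes move together, as expected when an any-change display sits beside a threshold display.

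**Step 3. The candidate repairs.** With 8b as ≤ −5, −4 to 4, ≥ 5, every 8a class lies in one 8b class and none is split. Keeping 8b and moving the 8a edges to 6 (for example 1 to 5, ≥ 6, −5 to −1, −9 to −6, and so on) also removes the splits, but the inner classes then hold five integer values rather than four.

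**Step 4. How many participants are affected?** The documents give no mean or SD for mRSS change in this trial, so these are assumptions: mean μ from −3 to −5, SD σ from 5 to 8, normal and rounded to whole numbers.

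- P(change = −5) = Φ((−4.5 − μ)/σ) − Φ((−5.5 − μ)/σ). Lowest at μ = −3, σ = 8: 0.4256 − 0.3773 = 4.8%. Highest at μ = −5, σ = 5: 0.5398 − 0.4602 = 8.0%.
- P(change = +5), by the same method: 1.1% (μ = −5, σ = 5) to 3.0% (μ = −3, σ = 8).
- Proportion improved: 38–54% if −5 counts, 31–47.5% if it does not.
- Proportion worsened: 3–17% if +5 counts, 2–14% if it does not.

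Denominator: the model in SAP 10.1 indexes 51 patients, and Table 7.1 plans 24% cumulative dropout at month 18. 51 × 0.76 = 38.8, about 39. Then 39 × 4.8% = 1.9 and 39 × 8.0% = 3.1, so about 2–3 participants sit at exactly −5, both arms together. At +5 the expected number is 0.4 to 1.2. If all 51 had month-18 data, the numbers at −5 would be 2.5 to 4.1.

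**The case against.** The strongest reply is that 8a and 8b are separate displays with separate purposes: a histogram of any change and a threshold summary. They disagree by design at ±1 to ±4, and would still do so after any repair. That stands. A reader might infer that the SAP states one rule twice in contradictory forms, or that the repair would stop a participant being improved in one table and unchanged in the other. Neither follows. The defect is narrower: two 8a classes cannot be collapsed into 8b.

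Second, the strict cut may be deliberate. The QILD-WL grouping has the same shape, with an inclusive stable band, and Section 14, change f, says that clinically meaningful cutpoints were considered. This stands as far as it goes. SAP practice is mixed, however: the FVC-% grouping in item 7b puts the edge value in the outer classes. No source is given for the mRSS cut.

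Third, a reader might infer from Protocol 2.1.2 that 5 units is the documented threshold for meaningful skin improvement. It is not. That passage describes how large most SLS II improvements were, and gives no minimal important change for mRSS.

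Fourth, the consequence is small. Change f describes "using the frequency table and bar chart to demonstrate the frequency distribution of the secondary endpoints", with no test attached, and the numeric limits printed beside the label show the direction. That stands too, and it limits the size of the point. It does not make the label correct.

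Two further inferences are not errors in the plan. Participants with a low baseline score cannot reach *improved*, but that is true of any absolute threshold, and moving the edge to −5 would help only those with a baseline of exactly 5. The three-class summary is not planned separately for diffuse disease, but the SAP already plans a diffuse-disease distribution and box plot, and 8.3 plans no subgroup analyses.

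**Conclusion.** The point holds in this limited form. The label in 8b is wrong as written, and the same wording recurs in 10.2.2 item 11 and Section 14, change f. The edges of 8a and 8b are misaligned by one integer on each side. The documents do not say which edge was intended.

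The cost is a misleading row heading and a shift in the reported proportion improved of about 5–8 percentage points, or roughly 2–3 participants in all. Those figures rest on the assumed mean, SD and normal shape, and on the planned attrition applying to 51 participants. Nothing inferential changes: mRSS is tested as a continuous change in the mixed model of 10.2.2 item 1, and the primary FVC-% analysis and the power calculation do not use these classes.

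**What to change.** In SAP 5.2.2 item 8b and 10.2.2 item 11, and in the copy in Section 14, change f:

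1. Replace *decreased* with *worsened*.
2. Align the edges so that the 8a classes sum to the 8b classes. The simplest form is improved (≤ −5), no change (−4 to 4), worsened (≥ 5). It leaves 8a untouched and matches the grouping of 5 units or more used descriptively in Protocol 2.1.2. If the strict cut was intended, keep 8b, move the 8a edges to 6, and give the reason.

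Choose the edge before unblinding, since a later choice could be informed by the data. If the data are already unblinded, record the change as a dated correction and show the proportions under both edges.

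The cost is a few words of SAP text and the matching table programs. No new data are needed.

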### 5.2.3 Other Endpoints

1. The change from baseline to month 18, measured at 6-month intervals, in PROMIS-29 version 2.0 with the following domains: Physical Function, Anxiety, Depression, Fatigue, Sleep Disturbance, Pain Interference, Impact on Social Roles, and a single item on pain intensity.
2. The proportion of participants in each treatment from screening to month 18 with a 2% increment in QILD-WL. It is also categorized as better (<-2%), stable ( $\geq -2\%$ ,  $\leq 2\%$ ) and worsen (>2%).
3. The proportion of participants in each treatment arm with a 3% or greater decline from baseline in FVC-% over the 18-month treatment period.
4. The proportion of participants in each treatment arm with a 5% or greater decline from baseline in FVC-% over the 18-month treatment period.
5. The change from baseline to month 6, 12, and 18 in patient global assessment of “overall health” in the past week.
6. Patient transition questions of global assessment at month 6, 12, and 18 comparing their i) overall

health and ii) lung involvement to that at the baseline visit.

7. The change from baseline to month 6, 12, and 18 in supplemental questions in Leicester Cough Questionnaire (LCQ) regarding the cough severity, cough frequency and phlegm production.

## 6 Study Methods

### 6.1 General Study Design and Plan

This study is designed as a phase II multi-center, double-blind, parallel group, randomized and placebo-controlled clinical trial addressing the treatment of patients with active and symptomatic SSc-ILD. Eligibility for the study was assessed during a 3-month screening period. Eligible participants were randomized in a 1:1 assignment to receive either oral MMF and Plac (acting as a control arm) or a combination of oral MMF and oral PFD (acting as an experimental arm), with both regimens administered for 18 months.

MMF was administered orally twice daily with a 4-step titration at monthly intervals to a target dose of 1500 mg twice daily as tolerated. PFD/PBO was administered orally three times daily with a 3-step titration at 2 week intervals to a target dose of 801 mg three times daily as tolerated. Patients could receive ongoing treatment with a maximum tolerated dose for either drug that was less than the target dose according to rules defined by the protocol. MMF is approved for use as an immunosuppressant in solid organ transplantation (cardiac, hepatic and renal) at doses up to 1.5 g twice daily and for the treatment of Lupus nephritis, an autoimmune manifestation of systemic lupus erythematosus, in the dose range of 1 to 3 g daily. PFD is currently approved for the treatment of IPF at a recommended dose of 801 mg (3 capsules of 267 mg each) 3 times daily. They were administered in this study at doses that fall within these FDA-defined dosing ranges but as experimental therapy for SSc-ILD.

A participant was considered to have completed the study if he or she completed all phases of the study including the last visit, or the last scheduled procedure, regardless of the dose of either study drug. Participants were followed in the study even if study drug was prematurely discontinued unless they had withdrawn their consent to do so. End of study was constituted by completion of the entire potential 18 months in all randomized participants.

### 6.2 Inclusion-Exclusion Criteria and General Study Population

#### 6.2.1 Inclusion Criteria

In order to be eligible for randomization as a study participant, an individual must have met all of the following inclusion criteria. Patients were provided consent prior to the screening and screening was included as part of the consent process.

#### Screening criteria that met prior to moving forward to HRCT imaging

1. Age >18 years
2. Scleroderma as determined by the 2013 ACR/EULAR classification criteria.
3. Grade  $\geq 2$  on the Magnitude of Task component of the Mahler Modified Dyspnea Index (Becomes short of breath with moderate or average tasks such as walking up a gradual hill, climbing less than three flights of stairs, or carrying a light load on the level).

4. FVC-% of  $\leq 85\%$  at screening. (The original cutpoint was  $<80\%$ ; the cutpoint was changed in protocol amendment version 1.2 [December 1, 2021] to  $\leq 85\%$ .)
5. Onset of the first non-Raynaud manifestation of SSc within the prior 84 months.

Screening HRCT imaging

6. Presence of any ground glass opacification (any GGO) on thoracic HRCT

Final screening criteria fulfilled at Baseline Visit, but prior to randomization

7. Repeat FVC-% at the baseline visit within 10% of the FVC-% value measured at screening. If these criteria are not met, a repeat FVC-% may be obtained within 7 days and the subject may qualify for randomization if the repeat FVC-% agrees within 10% of the FVC-% obtained at screening.

### **6.2.2 Exclusion Criteria**

An individual who met any of the following criteria was excluded from participation in this study. The majority of exclusion criteria were assessed at screening, unless explicitly stated.

1. Disease features supporting the primary diagnosis of another connective tissue disease such as rheumatoid arthritis, systemic lupus erythematosus or mixed connective tissue disease (Features consistent with a secondary Sjogren syndrome or scleroderma-associated myopathy were allowed).
2. FVC-%  $<45\%$  at either screening or baseline.
3. FEV1/FVC ratio  $<0.65$  at either screening or baseline.
4. DLCOHb-% of  $<30\%$  at screening or  $<25\%$  at baseline.
5. Diagnosis of clinically significant resting pulmonary hypertension or mild pulmonary hypertension requiring treatment with more than one oral medication as ascertained prior to study evaluation or as part of a standard of care clinical assessment performed outside of the study protocol.
6. Evidence of uncontrolled congestive heart failure, unstable ischemic heart disease, history of complicated pulmonary embolism impacting on heart or lung function, or unstable cardiac arrhythmia requiring chronic anticoagulation.
7. Clinically significant abnormalities on HRCT not attributable to SSc.
8. Hematologic abnormality at screening including:
  - a. Leukopenia (white blood cells [WBC]  $<4.0 \times 10^3/\mu\text{l}$ ),
  - b. Thrombocytopenia (platelet count  $<120.0 \times 10^3/\mu\text{l}$ ),
  - c. Clinically significant anemia [Hemoglobin (Hgb)  $<10.0 \text{ g/dl}$ ].

Participants with an identified and correctable etiology may have been eligible if repeat testing within the maximal 90-day screening period met all criteria.

9. A diagnosis of chronic liver disease or abnormal baseline liver function test (LFTs) or total bilirubin that were  $>2.0 \times$  upper normal limit.
10. Serum creatinine  $>2.0 \text{ mg/dl}$ .
11. History of recurrent aspiration, uncontrolled heartburn, or gastroesophageal reflux disease with a reflux scale score of  $>1.00$  as determined by a UCLA Scleroderma Clinical Trial Consortium Gastrointestinal Scale (UCLA SCTC GIT), Version 2.0.  
Participants with uncontrolled heartburn or GERD that was amenable to medical management may have been eligible if repeat testing within the maximal 90-day screening period met this criteria.
12. Known achalasia, esophageal stricture or esophageal dysfunction sufficient to limit the ability to swallow medication.
13. Pregnancy (documented by serum pregnancy test) and/or breast feeding.
14. If of child bearing potential (a female participant  $<55$  years of age who had not been postmenopausal for  $\geq 5$  years or who had not had a bilateral salpingectomy, hysterectomy and/or oophorectomy),

failure to employ two reliable means of contraception which may include surgical sterilization, barrier methods, spermicides, intrauterine devices, and/or hormonal contraception, unless the participant chooses abstinence (to avoid heterosexual intercourse completely). If a subject chose abstinence, then a second reliable means of contraception was not needed.

15. Prior use of potential disease modifying antirheumatic drugs (DMARDs) according to the following exposure rules:
  - a. Use of oral cyclophosphamide (CYC), MMF, azathioprine or other oral or short half-life DMARDs for more than 6 months in the past year, as determined at the time of the initial screening visit.
  - b. Treatment with more than three intravenous doses of CYC, more than one course of Rituximab or other intravenous or injectable DMARDs in the past year.
  - c. More distant history of treatment with a DMARD was allowed as long as the patient had a new diagnosis/new episode of active SSc-ILD since stopping that treatment and mets the criteria noted in 15a or 15b.
16. Use of CYC, MMF, azathioprine, Rituximab or other DMARD in the 30 days prior to the baseline visit unless the patient is on MMF and the responsible physician indicated that continued use was in the best clinical interest of the patient.
17. Active infection (lung, ulcers or elsewhere) whose management would be compromised by immunosuppression.
18. Other serious concomitant medical illness (e.g., active malignancy within the past 5 years other than surgically-removed local skin cancer such as a basal cell carcinoma), chronic debilitating illness (other than SSc), unreliability or drug abuse that might compromise the patient's participation in the trial.
19. Current use, or use within the 30 days prior to their baseline visit, of prednisone (or equivalent) in doses >10 mg/day.
20. Smoking of cigars, pipes, or cigarettes during the past 6 months.
21. Use of contraindicated medications, including medications with putative disease-modifying properties that do not meet the exposure limits described in Exclusion Criteria #15 and #16, moderate or strong inhibitors of cytochrome P450 (CYP) isozyme 1A2 (CYP1A2) (note ciprofloxacin allowed up to a dose of 500 mg twice daily), and moderate inducers of CYP1A2 (such as tobacco smoke or phenytoin).

